**5.5.2. Immunohistochemical analysis of pre- vs. post-Letrozole tumors.**  
Baseline (diagnostic core biopsy specimen) and post-Letrozole (surgical specimen) tumor samples will be sectioned and processed for IHC in the Pathology Translational Research Shared Resource. Tissue sections will be immunostained using antibodies against ER, PR, and Ki67. ER and PR

will be scored using a Histoscore scale (23); we expect Letrozole treatment to decrease PR levels, while ER may be unaffected. Ki67 will be scored by counting the number of positively-stained cells in 10 high-power (400x magnification) microscopic fields (24, 25). Pre- and post-Letrozole Ki67+ cell counts will be compared by t-test; Letrozole treatment should induce an overall decrease in Ki67 score.

The primary goal of this analysis is to determine whether changes in signaling induced by RAD001 treatment *ex vivo* are associated with Ki67 score. A higher post-anti-estrogen Ki67 score, and a smaller decrease in Ki67 score in response to presurgical treatment with an anti-estrogen, are associated with shorter recurrence-free survival (26). Hence, it is thought that a higher level of residual tumor cell proliferation (higher Ki67 score) following anti-estrogen treatment, or a weaker biological response (change in Ki67 score) to anti-estrogen treatment, are indicative of less dependence of tumor cells on ER for growth and survival. Our preclinical data indicate that ER drives IRS-1 and IGF-1R expression, which facilitate RAD001-induced PI3K/AKT activation. Therefore, in tumors that are less dependent upon ER, Letrozole treatment is expected to have less of an effect on IRS-1/PI3K/AKT signaling. Such findings would support the use of combinations of anti-estrogens and mTORC1 inhibitors in patients with ER-driven tumors.

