### 1.2. The presurgical study model

An initial diagnosis of breast cancer is typically made by histological confirmation of a tissue biopsy specimen. Patients with Stage I-III cancer will then typically undergo surgery within a few weeks to remove the primary tumor(s). Therefore, it is common to have a paired tumor biopsy specimen and a surgical tumor specimen. The availability of such paired specimens has prompted a large initiative in recent years to treat patients (e.g., with drug) during the intervening period between the time of diagnostic biopsy and the time of surgery. We can then compare the biopsy tissue (baseline, pre-treatment) to the surgical tissue (post-treatment) to assess biological changes (e.g., changes in mRNA and protein expression). This study design has provided a wealth of information on the effects of systemic therapies on tumor biology [reviewed in ref. (1)], and it requires no additional biopsy procedure.

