### 2.2 Secondary objectives

1. To determine whether presurgical treatment with Letrozole suppresses IRS-1/PI3K/AKT pathway activation compared to baseline.
2. To determine whether the level of IRS-1/PI3K/AKT pathway activation is correlated with rate of tumor cell proliferation as determined by Ki67 score.
3. To determine whether RAD001-induced changes in IRS-1/PI3K/AKT signaling *ex vivo* are correlated with rate of tumor cell proliferation as determined by Ki67 score.
4. To identify changes in mRNA levels of ER-regulated gene induced by presurgical treatment with Letrozole.

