## 3.0 ELIGIBILITY CRITERIA

### **Inclusion Criteria:**

- 3.1. Histologic documentation of invasive breast cancer by core needle or incisional biopsy. Excess baseline biopsy tumor tissue sufficient to make three 5-micron sections must be available for molecular analyses as part of this study.
- 3.2. The invasive cancer must be estrogen receptor alpha (ER)-positive, with ER staining present in greater than 50% of invasive cancer cells by IHC
- 3.3. The invasive cancer must be HER2-negative (IHC 0-1+, or with a FISH ratio of <1.8 if IHC is 2+ or if IHC has not been done).
- 3.4. Clinical Stage I-III invasive breast cancer with the intent to treat with surgical resection of the primary tumor. Tumor must be  $\geq 2$  cm to provide adequate tissue.

- 3.5 Patients with multicentric or bilateral disease are eligible if the target lesions meet the other eligibility criteria. Samples from all available tumors are requested for research purposes.
- 3.6. Women  $\geq$  age 18, for whom adjuvant treatment with an aromatase inhibitor would be clinically indicated. Women must be either post-menopausal, or pre-menopausal having undergone oophorectomy.
- 3.7. Patients must meet the following clinical laboratory criteria:
  - Absolute neutrophil count (ANC)  $\geq$  1,000/mm^3 and platelet count  $\geq$  75,000/mm^3.
  - Total bilirubin  $\leq$  1.5  $\times$  the upper limit of the normal range (ULN).
  - Alanine aminotransferase (ALT) and aspartate aminotransferase (AST)  $\leq$  3  $\times$  ULN.
- 3.8. Ability to give informed consent.

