Immunohistochemistry (IHC) on frozen tissues- Two cores each of DMSO- and RAD001-treated tumor will be sectioned and processed for IHC in the Pathology Translational Research Shared Resource. Tissue sections will be immunostained using antibodies against phospho-S6-Ser240/244, phospho-AKT-S473, phospho-AKT-T308 and phospho-IGF-1Rb/InsR- Tyr1131/Tyr1146. Samples will be scored using a Histoscore scale that incorporates staining intensity and frequency (12).

The primary goal of this analysis is to determine whether RAD001 treatment *ex vivo* decreases mTORC1 signaling (indicated by a decrease in levels of phospho-S6) and increases AKT phosphorylation uniformly throughout tumor cores, and whether drug treatment alters IGF-1R/InsR phosphorylation (which cannot be assessed by immunoblot analysis of protein lysates). Staining intensities in the center of each core will be compared to the outer edges to assess uniformity of signal; non-uniformity may be due to time of exposure of cells to drug or medium.

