## 9.0 STATISTICAL CONSIDERATIONS

9.1 PRIMARY ENDPOINT – The primary endpoint of this trial is the level of IRS-1/PI3K/AKT pathway activation in primary tumors, measured by densitometric analysis of immunoblot signals of markers of pathway activation (IRS-1, phospho-IRS-1-Ser636/639, phospho-AKT-T308, phospho-AKT-S473).

9.2 SECONDARY ENDPOINT – The secondary endpoint is Ki67 score, as determined by the percentage of Ki67+ tumor cells by IHC.

9.3 PRIMARY ANALYSIS PLAN - The primary analyses determine whether RAD001 treatment of tumor samples *ex vivo*, and/or presurgical treatment of patients with Letrozole, alter IRS-1/PI3K/AKT pathway activation in breast tumors. Signal values of IRS-1, phospho-IRS-1-Ser636/639, phospho-AKT-T308, phospho-AKT-S473 will be determined by densitometric analysis of immunoblots. Below is an illustration of projected data and relevant comparisons. Signal values of control (DMSO)-treated and RAD001-treated tumor samples will be compared using a 2-sided paired t-test. These tests will be performed separately in tumors from each arm of the study (*i.e.*, untreated, or letrozole-treated, as shown below in *left* and *center* panels). An additional test will compare the magnitude of change in signal values in Arm A vs. Arm B (2-sided independent t-test), to determine whether Letrozole treatment alters response to RAD001 (shown below in *right* panel).

9.4 SECONDARY ANALYSIS PLAN – Secondary analysis to determine whether presurgical treatment with Letrozole suppresses IRS-1/PI3K/AKT activation compared to baseline will be achieved using a paired t-test comparing IRS-1/PI3K/AKT pathway markers scored by IHC analysis of matching tumor samples from patients acquired A) at baseline (diagnostic biopsy) and B) at surgery (post-Letrozole). We will also determine whether tumor Ki67 IHC score is associated with the level of IRS-1/PI3K/AKT pathway activation, or with RAD001-induced changes in IRS-1/PI3K/AKT signaling, by Spearman correlation between Ki67 score and densitometric signal values of pathway markers as determined by immunoblot analysis or IHC Histoscore.

9.5 STATISTICAL TESTING - All statistical tests will be 2-sided, and the overall type I error will be 0.05.

9.6 SAMPLE SIZE – The primary analyses determine whether RAD001 treatment of tumor samples *ex vivo*, and/or presurgical treatment of patients with Letrozole,

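### Section 5.5.2 does not list the pathway markers that 9.4 tests on biopsy and surgical tissue, and it scores Ki67 as a count where 9.2 defines a percentage

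*Combined protocol and SAP*

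**What the plan says.** **Pathway markers.** The first secondary objective in 2.2 is "To determine whether presurgical treatment with Letrozole suppresses IRS-1/PI3K/AKT pathway activation compared to baseline". Section 9.4 assigns it a "paired t-test comparing IRS-1/PI3K/AKT pathway markers scored by IHC analysis of matching tumor samples from patients", with the diagnostic biopsy as the baseline member and the post-Letrozole surgical specimen as the other. Section 9.4 does not say which markers are stained. Section 5.5.2 is the assay section for this pair of specimens, and its whole stain list is: "Tissue sections will be immunostained using antibodies against ER, PR, and Ki67".

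Pathway markers are stained by IHC in 5.5.1, but on different material: "Two cores each of DMSO- and RAD001-treated tumor will be sectioned and processed for IHC". That panel begins "Tissue sections will be immunostained using antibodies against phospho-S6-Ser240/244, phospho-AKT-S473, phospho-AKT-T308" and adds one phospho-IGF-1R/InsR antibody. It contains neither IRS-1 nor phospho-IRS-1.

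On baseline tissue, criterion 3.1 states: "Excess baseline biopsy tumor tissue sufficient to make three 5-micron sections must be available".

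**Ki67.** Section 9.2 makes Ki67 score the secondary endpoint and defines it as the percentage of tumour cells that are positive. Section 5.5.2 states: "Ki67 will be scored by counting the number of positively-stained cells in 10 high-power (400x magnification) microscopic fields". It then compares the pre- and post-Letrozole counts by a t-test that it does not describe as paired.

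**The concern.** Section 1.2 sets out the logic of the design: "We can then compare the biopsy tissue (baseline, pre-treatment) to the surgical tissue (post-treatment) to assess biological changes". For the pathway, that comparison needs the same markers measured on both specimens. The analysis section assumes such measurements exist, but the assay section does not order them. Baseline tissue is limited. If a patient enters with the minimum and her sections go to ER, PR and Ki67, her baseline pathway value may not be recoverable. One of the four secondary objectives is exposed.

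For Ki67, a count in a fixed number of fields equals the proliferating fraction multiplied by the number of tumour cells in those fields. Core biopsies and surgical specimens may differ in tumour-cell density. The cellularity requirement in 5.2.1 and 5.4 (at least 50%) applies only to the surgical specimen. A systematic density difference would bias the pre/post comparison of counts. Random density variation would add noise and cost power.

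**Working it through.** The plan states no figure on this point, so there is none to reproduce. The check is a comparison of sections, a section count and an illustrative simulation.

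**Step 1. Which assay covers which tissue**

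| Assay | Tissue | Markers | Baseline biopsy? |
|---|---|---|---|
| 5.5.1 immunoblot | surgical cores cultured with DMSO or RAD001 | IRS-1, phospho-IRS-1, both phospho-AKT sites and others | no |
| 5.5.1 IHC | surgical cores cultured the same way, then frozen | phospho-S6, two phospho-AKT sites, phospho-IGF-1R/InsR | no |
| 5.5.2 IHC | biopsy and surgical specimen | ER, PR, Ki67 | yes |
| 9.4 paired test needs | biopsy and surgical specimen | IRS-1/PI3K/AKT markers, not named | yes |

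No assay section supplies the last row. The DMSO cores in 5.5.1 carry phospho-AKT IHC, but they have been cultured ex vivo and have no baseline counterpart.

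**Step 2. Baseline sections, assuming one antibody per section** (the documents do not say this)

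- Guaranteed by 3.1: 3. Used by ER, PR and Ki67: 3. Left: 3 − 3 = 0.
- With phospho-AKT-S473 and phospho-AKT-T308: 3 + 2 = 5.
- With all four markers of 9.1 (IRS-1, phospho-IRS-1, two phospho-AKT sites): 3 + 4 = 7.

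**Step 3. Count against percentage**

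Expected count = Ki67 fraction × tumour cells in the 10 fields. At a constant 20% and an assumed 5,000 cells the count is 0.20 × 5,000 = 1,000. At 3,500 cells it is 700, a 30% fall with no change in the percentage.

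**Step 4. Illustrative simulation.** Every input is assumed: median Ki67 20%; log-SD 0.5 between patients and 0.2 per specimen within patient; mean 2,000 tumour cells per 10 fields, lognormal with CV 0.2 to 0.4 and independent between the two specimens; binomial counts; two-sided paired t-test at 0.05. The sample sizes are the Arm B sizes in 9.6. Ranges run over the two CVs.

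*No true change in percentage: proportion of trials falsely significant*

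| Surgical/biopsy density | n=10, counts | n=14, counts | n=30, counts | percentages, all n |
|---|---|---|---|---|
| 1.0 | 3.9–4.2% | 4.1–4.4% | 4.5–4.7% | about 4–5% |
| 0.9 | 6.0–9.2% | 7.2–12.3% | 12.0–23.0% | about 4–5% |
| 0.75 | 19.6–42.0% | 28.1–59.1% | 57.1–91.5% | about 4–5% |

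*No systematic density shift: power, counts versus percentages*

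| True change | n=10 | n=14 | n=30 |
|---|---|---|---|
| 20% to 15% | 19–42% vs 69% | 28–59% vs 86% | 57–91% vs over 99% |
| 20% to 10% | 75–97% vs over 99% | 90–99.8% vs over 99% | over 99% for both |

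If densities in a patient's two specimens correlate at 0.5, power on counts for the fall to 15% at n=10 rises to 29–52%.

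**The case against.** The strongest reply on the pathway markers is that 9.4 itself calls for the assay. It states the tissue, the method, the pairing and the test; 5.5.2 does not say its antibody list is complete; and 5.2.1 collects uncultured frozen and FFPE surgical cores. This stands. A reader might infer that objective 1 has no data at all. The documents support only a conditional version: the data are missing if 5.5.2 is followed on its own. What the reply does not supply is a marker panel, which no section names for this pair.

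A reader might also infer that baseline tissue is short. Three sections is an entry minimum, not a cap or an expected yield, and one antibody per section is an assumption. What is missing is a guarantee of tissue.

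On Ki67, a reader might infer that the Spearman analyses for objectives 2 and 3 rest on counts. Section 9.4 uses the term Ki67 score, which 9.2 defines as a percentage, so the natural reading is that they use the percentage. They are affected only if the 5.5.2 count is taken as the score.

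It is also fair to say that the pre/post Ki67 t-test appears only in 5.5.2 and serves none of the four listed secondary objectives. The power loss shrinks greatly with a larger effect or larger n. Nothing in the documents shows that density shifts between specimens, so they give no ground for saying that type I error is inflated.

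**Conclusion.** Two inconsistencies stand, both in secondary analyses.

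(a) The pathway panel for the biopsy/surgical pair is unnamed in 9.4 and absent from 5.5.2. If the laboratory follows 5.5.2 alone, there are no baseline pathway data and objective 1 cannot be tested. If one antibody is used per section, the minimum in 3.1 does not guarantee tissue for any stain beyond ER, PR and Ki67.

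(b) Ki67 has two definitions. The count in 5.5.2 is the worse measure: it can be biased if density differs systematically between specimens, and it loses power if density varies at random. The sizes shown depend wholly on the assumed model, because the documents give neither density data nor an expected fall in Ki67. With no systematic shift, false positives are not inflated.

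No primary endpoint, sample size or alpha is affected. The point is worth settling before Arm B tissue is sectioned.

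**What to change.** **Pathway markers.** In 5.5.2 and 9.4, name one panel to be stained on both specimens, state Histoscore scoring, and specify comparable surgical material (uncultured, with the same fixation as the biopsy). Then check 3.1 against the chosen panel. At one antibody per section, phospho-AKT-S473 and -T308 bring the total to 5 sections but cover only AKT activation; all four 9.1 markers bring it to 7. Allow as well for anything the mRNA objective draws from the same biopsy. If the tissue does not permit this, narrow objective 1 to what can be stained, or delete it with its test. The cost is two to four extra stains per specimen and possibly fewer patients with enough baseline tissue.

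**Ki67.** In 5.5.2, count total tumour cells in the same 10 fields, use percent positive as in 9.2 throughout (including the 9.4 correlations), and state that the pre/post comparison is a paired t-test. The cost is a wording change and some extra counting in fields already being read.

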## 6.0 DATA COLLECTION, HANDLING AND RECORD KEEPING

### 6.1. Confidentiality

Information about study subjects will be kept confidential and managed according to the requirements of the Health Insurance Portability and Accountability Act of 1996 (HIPAA). Participants will sign an authorization that includes the following:

- What protected health information (PHI) will be collected from subjects in this study
- Who will have access to that information and why
- Who will use or disclose that information
- The rights of a research subject to revoke their authorization for use of their PHI.

In the event that a subject revokes authorization to collect or use PHI, the investigator, by regulation, retains the ability to use all information collected prior to the revocation of subject authorization.

Loss of patient confidentiality is a risk of participation. Study participant identities will be kept confidential except as required by law. Subjects' samples will be identified by code only (i.e., linked, but de-identified). Patient samples will be de-identified at the time and site of collection. Participant and study information will be kept in the Velos eResearch password-protected database or its equivalent. Additionally, documents containing participant identifiers, such as those from the medical record to confirm eligibility, will be filed in binders and

kept in a locked, secure location in the Office of Clinical Research at the Norris Cotton Cancer Center.

#### 6.2. Data retention

Following closure of the study, the investigator will maintain all site study records in a safe and secure location. The records are maintained to allow easy and timely retrieval, when needed (e.g., audit or inspection) and, whenever feasible, to allow any subsequent review of data in conjunction with assessment of the facility, supporting systems, and staff. Upon completion of study analysis, research information is stored in Dartmouth College Records Management off-site storage located at [name]. Documents are shredded on site after 50 years of storage.

Participant and study information will be kept in the Velos eResearch password protected database (or its equivalent) indefinitely.

### 7.0 STUDY MONITORING, AUDITING, AND INSPECTING

#### 7.1 Safety and Data Monitoring

This study will be monitored by the Data Safety Monitoring and Accrual Committee (DSMAC) of the Norris Cotton Cancer Center. The Committee meets quarterly to review accrual rates and information of all studies that have accrued participants. The DSMAC has the authority to suspend or terminate all research activities that fall within its jurisdiction. In the event that a study is suspended or terminated by the DSMAC, that information will be forwarded to the CPHS office.

#### 7.2 On-Site Monitoring

Clinical research monitoring will be conducted by appropriately trained staff of Dartmouth-Hitchcock Medical Center Clinical Trials Office. This monitoring will include periodic assessment of the regulatory compliance, data quality, and study integrity. Study records will be reviewed and directly compared to source documents and the conduct of the study will be discussed with the investigator. Monitors may request access to all regulatory documents, source documents, CRFs, and other study documentation for on-site inspection. Direct access to these documents is guaranteed by the investigator, who must provide support at all times for these activities.

#### 7.3 Auditing and Inspecting

Participation as an investigator in this study implies acceptance of potential inspection by government regulatory authorities and applicable Dartmouth compliance and quality assurance offices. The investigator will permit study-

related audits and inspections by the Dartmouth CPHS, government regulatory bodies, and Dartmouth compliance and quality assurance groups of all study related documents (e.g. source documents, regulatory documents, data collection instruments, study data etc.) The investigator will ensure the capability for inspections of applicable study-related facilities (e.g. pharmacy, diagnostic laboratory, etc.)

## 8.0 ADVERSE EVENT REPORTING

Patients on Arm B will be instructed to report the occurrence of any adverse event (this will not apply to participants on Arm A). An adverse event is any undesirable event associated with the administration of letrozole. Adverse events will be graded according to the NCI Common Toxicity Criteria Version 4.0. A copy of the CTC version 4.0 can be downloaded from the CTEP home page (<http://ctep.info.nih.gov>). All appropriate treatment areas should have access to a copy of the CTC version 4.0.

This trial will be independently monitored by the Norris Cotton Cancer Center Data Safety and Accrual Monitoring Committee.

The following definitions will be used to assess causality:

No: The clinical adverse event is definitely unrelated to the study medications (e.g., does not follow a reasonable temporal sequence from study medication administration, present prior to receiving study medication, etc.)

Unlikely: The study medications do not have any reasonable association with the observed experience; however, relationship cannot be definitely excluded.

Possibly: The connection with study medication administration appears feasible, but cannot be excluded with certainty (e.g., follows a reasonable temporal sequence from medication administration, but may also be related to other known factors).

[figure not shown]
Probably: The clinical experience appears related to the study medications with a high degree of certainty (e.g., follows a reasonable temporal sequence from medication administration and abates upon discontinuation of the medication, cannot be reasonably explained by known characteristics of the patient's clinical state or other modes of therapy administered to the patient, etc.)

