#### Toxicities of letrozole

Most adverse reactions to letrozole in the literature are mild to moderate in severity and are indistinguishable from the consequences of the patient's metastatic breast cancer, the effects of estrogen deprivation, or other concurrent illness.

Reported events in greater than 5% of subjects include chest pain, hypertension, edema, hyperlipidemia, cough, dyspnea, nausea, vomiting, abdominal pain, anorexia, increased appetite, constipation, diarrhea, weight gain, weight loss, bone fractures, arthralgias, arthritis, back pain, bone pain, breast pain, myalgias, weakness, asthenia, dizziness, depression, fatigue, headache, insomnia, lethargy, malaise, rash, hot flashes, sweats, vaginal bleeding, vaginal dryness, and infections.

Letrozole will be prescribed by the subject's oncology provider and the subject will be asked to fill the prescription at her commercial pharmacy.

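### Section 8.0 defines an adverse event by its association with letrozole, which conflicts with a causality scale that includes unrelated events

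*Combined protocol and SAP*

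**What the plan says.** Everything at issue is in Section 8.0 (Adverse Event Reporting) of the combined protocol and SAP.

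- **Who reports.** "Patients on Arm B will be instructed to report the occurrence of any adverse event". Arm A is exempt.
- **Definition.** "An adverse event is any undesirable event associated with the administration of letrozole".
- **Grading.** "Adverse events will be graded according to the NCI Common Toxicity Criteria Version 4.0".
- **Causality category 'No'.** "The clinical adverse event is definitely unrelated to the study medications". Its examples include an event out of temporal sequence with dosing and one "present prior to receiving study medication".
- **Causality category 'Unlikely'.** "The study medications do not have any reasonable association with the observed experience", with the proviso that a relationship cannot be definitely ruled out.

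The scale continues with 'Possibly' and 'Probably', which raise no difficulty here. No other section gives a broader definition of an adverse event or says that events are to be recorded whatever their presumed cause. Section 7.1 gives oversight to the monitoring committee, and Section 7.2 provides for study records to be checked against source documents.

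**The concern.** A causality scale is useful only if events are captured first and attributed afterwards. Here the definition can be read as putting attribution first: an event must already be linked to letrozole before it counts as an adverse event. The scale then asks the assessor to say whether it is linked, and offers answers that the definition appears to have ruled out.

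The definition also governs what is collected. Patients are asked to report adverse events and adverse events are what is graded, so both duties inherit its limits. A patient or site that follows it closely could leave out an event attributed at first sight to something else, while another might report it. What is at stake is the completeness and consistency of the Arm B safety information reaching the committee.

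**Working it through.** No arithmetic bears on the contradiction, and the plan states no figure to reproduce. The check sets the definition beside the two lower causality categories under each plausible meaning of 'associated'.

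**Reading 1: 'associated' is causal.** The wording of 'Unlikely' supports this reading, because it uses 'association' in that sense.

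- 'No': an event must be linked to the drug to be an adverse event, yet this category requires it to be definitely unrelated. No event can satisfy both.
- 'Unlikely': an event must be associated with the drug, yet this category requires that there be no reasonable association. No event can satisfy both.

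Both categories are therefore empty.

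**Reading 2: 'associated' is temporal**, meaning an event that arises while letrozole is being taken.

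- 'Unlikely' has members: events during dosing for which a drug relationship is implausible but not excluded.
- 'No' also has members: for example, an event during dosing with an evident separate cause.
- Two of the examples under 'No' still conflict with the definition. An event out of temporal sequence with dosing, or one "present prior to receiving study medication", is not associated with dosing in time and so would not be an adverse event.

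The conflict is thus of whole categories under Reading 1 and of two illustrations under Reading 2. Neither reading removes it entirely.

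**Can association be judged when an event is first noticed?** Section 5.2.3, under the toxicities of letrozole, says that most reactions reported in the literature cannot be told apart from the consequences of metastatic disease, "the effects of estrogen deprivation, or other concurrent illness". Metastatic disease does not apply to a Stage I-III population, and estrogen deprivation is itself an effect of the drug. The reference to other illness does apply: by the protocol's own account, a letrozole reaction may look like an unrelated complaint. That favours recording first and attributing later.

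**Extent of exposure.** Section 9.6 sets Arm B at 10, 14 or 30 patients if it opens, and Section 5.2.2 gives 10 to 21 days of letrozole. Treatment time therefore lies between 10 × 10 = 100 and 30 × 21 = 630 patient-days. The documents give no event rate, so the number of events affected cannot be calculated.

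**Effect on the analyses.** "The primary endpoint of this trial is the level of IRS-1/PI3K/AKT pathway activation in primary tumors". The secondary endpoint is Ki67 score (Section 9.2). No objective, endpoint, test or decision rule uses adverse events.

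**The case against.** The strongest reply is that 'associated with' is not 'caused by'. The section uses the vocabulary of relatedness in the causality scale, so the definition may mean no more than events during treatment. On that reading both lower categories can be used, and what remains is a mismatch with examples that are offered only as illustrations. This is a fair point. It rules out saying without qualification that two categories are empty. It does not settle the matter, because the scale itself uses 'association' causally and the reader is left to choose.

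The second reply is that nothing tells anyone to discard an event, and that authors who wrote 'No' and 'Unlikely' categories evidently expected such events to be recorded. This also stands. A reader might infer that events judged unrelated will be lost. The documents support only that they could be lost, or handled differently from patient to patient.

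Third, monitors compare study records with source documents under Section 7.2. That gives some protection, but the comparison is made against the protocol's own definition and does not widen it.

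Finally, letrozole at this dose is described as standard adjuvant therapy (Sections 5.2.2 and 10.3) and exposure is short. This limits the importance of the point but leaves the wording unresolved.

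**Conclusion.** The point holds as an internal contradiction: the text is wrong as written, and the severity is minor. The definition and the causality scale cannot both be applied as they stand. The extent of the conflict depends on what 'associated' means, and the plan does not say. The practical consequence is possible omission or inconsistent recording of events in the 10 to 30 patients of Arm B, and so less complete information for the monitoring committee. The primary and secondary analyses are unaffected.

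Two stronger conclusions might be drawn, and the documents support neither. One is that Arm B safety counts will be biased downward: no safety count, rate or comparison is planned, so there is no estimate to bias. The other is that an unexpected letrozole effect is the event most likely to be missed: nothing in the documents shows which kinds of event would be left out.

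The verdict assumes that Section 8.0 is the only rule on recording events. No other section of the documents supplies one.

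**What to change.** Replace the definition in Section 8.0 with one based on timing, for example: an adverse event is any undesirable event that occurs or worsens in an Arm B patient from the first dose of letrozole until study exit as described in Section 5.3, whether or not it is considered related to letrozole. Then assign causality with the existing scale.

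Two details need attention. The example under 'No' of an event that predates the drug must be reconciled with the new definition, for instance by limiting it to worsening of a pre-existing condition. The reporting period also needs a stated end. Section 5.3 ends the patient's role following surgery, so the definition should refer to that section.

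The cost is a small rewording of Section 8.0 and a few more events to record in 10 to 30 patients. Endpoints, sample size and the planned analyses do not change.
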